9.2. Secondary Outcome Measures

- To determine safety of administering Zepatier to heart transplant recipients who were previously HCV-negative, but developed de-novo HCV after receiving a heart transplant from an HCV-positive donor
- To determine 1-year graft survival rates of HCV-negative heart transplant patients who receive a heart transplant from a genotype 1 or 4 HCV-positive donor, including those who spontaneously clear HCV and those who receive open-label Zepatier upon development of de-novo HCV.
- To evaluate rates of spontaneous clearance of HCV among HCV-negative patients who receive a heart transplant from a genotype 1 or 4 HCV-positive donor.

9.2.1. Safety

Subject safety and adverse events will be based in CTCAE Version 4 criteria, listed in Section 13, and will include adverse events and serious adverse events, related both to receipt of a heart transplant from an HCV-positive donor among HCV-negative subjects with heart failure, and adverse events related to administration of Zepatier.

9.2.2. Graft Survival

Graft survival will be based on standardize United Network for Organ Sharing (UNOS) criteria, with a graft failure defined as subject death, or re-transplantation within the first year post-transplantation.

9.2.3. Spontaneous Clearance or Non-Transmission of HCV

Spontaneous clearance or non-transmission of HCV will be based on an undetectable HCV RNA level at post-transplant weeks 1-4 in the absence of treatment among HCV-negative subjects who receive a heart transplant from a confirmed genotype 1 or 4 HCV-positive donor. Any subject who experiences spontaneous clearance of HCV or non-transmission of HCV will still be tested for HCV RNA at weeks 8, 16, and 28, to ensure that their levels are still undetectable.

10 CHAPTER 7: STATISTICAL CONSIDERATIONS

10.1. Study Design

This open-label trial involves one primary and several secondary objectives. Post-transplant HCV status will be monitored, and patients will be treated with 12-16 weeks of Zepatier therapy, after which time, treatment will be complete, barring instances of treatment failure, which would require an additional 12 weeks of therapy.*

10.2. Disposition of Subjects and Baseline Comparisons

Summaries of all subjects screened, recruited, and enrolled will be provided, according to the CONSORT guidelines. The treatment groups will be evaluated at baseline with respect to demographics and baseline measurements related to efficacy and safety without formal statistical testing.

10.3. Analyses of Outcome Measures

The primary analysis will evaluate SVR-12 rates of HCV-negative heart transplant recipients who receive a heart from an HCV-positive donor and subsequently develop de-novo HCV. All patients will be assessed for toxicity and included in the safety analysis. This analysis will include summaries of the incidence and grade of toxicities. Patients will be evaluated for serious adverse events. Safety interim analyses will be performed and reported at each DSMB meeting.

10.4. Missing Data and Dropouts

We will attempt to minimize missing data, however we have planned for its occurrence. For subjects lost to follow-up, we will use all of the information available until the end of follow-up. Subjects who withdraw consent will no longer be followed in this protocol. Patients will receive care from the patients' clinicians.

For patients lost to follow-up, we will use all the information available up to the time of loss to follow-up. For the primary end point, we will perform an analysis of completers only. We will also perform additional sensitivity analyses using imputation to assess the impact of missing data for the primary and secondary end points.

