Number of subjects	Estimated 10 HCV-negative subjects transplanted with a heart from an HCV-positive donor
Plan for statistical analysis	
Primary endpoint:
 
 • Post-treatment sustained virologic response (SVR)

	
Secondary endpoints:
 
• Determine if there are major adverse events attributable to HCV therapy in post-heart transplant patients.• Evaluate 1-year heart graft survival in HCV-negative patients who receive a heart transplant from an HCV-positive donor• Determine the rates of spontaneous HCV clearance among HCV-negative patients with heart failure receiving a heart from an HCV-positive donor 
Data analysis:
 
The primary analysis will be based on a calculation of SVR rates (number of subjects with SVR-12; negative HCV RNA 12 weeks after completing Zepatier therapy) / (number of subjects treated with Zepatier post-heart transplantation)

--	---

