10.5. Protocol Violations

Serious protocol deviations such as discontinuation of experimental treatment unrelated to adverse events (AEs) will be carefully recorded and regularly reviewed by co-Principal Investigators. Remedial changes in procedure will be recommended where feasible to reduce the incidence of such deviations. The causes and circumstances of all violations will be documented where known for purposes of future secondary analyses and interpretation. Because all primary analyses will be intent-to-treat, it is essential that violations be kept to a minimum, especially where it is possible to influence their rate of occurrence. A missed study visit will not be considered a protocol violation unless the study drug was scheduled to be dispensed at the visit, the subject did not have necessary labs done, or the subject has not been stable.

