12.6. Other Events

We will not discontinue study drug for clinical events not thought to be serious drug-related AEs. For example, a hospitalization for clinical worsening may or may not result in cessation of trial participation. Such events could result in missing data for primary and secondary endpoints, comprising the integrity of the analysis. This trial does prohibit certain therapies, thus there may be a reason to stop study drug participation under such circumstances. Even if subjects are withdrawn from the study drug, outcome assessments will continue, allowing analysis by intent-to-treat.

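### The denominator for the primary SVR-12 rate is stated three ways (completers only, all treated, intent-to-treat), and nothing says which governs

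*Combined protocol and SAP*

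**What the plan says.** Three parts of the combined protocol and SAP describe the set on which the primary efficacy result is calculated.

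- **Synopsis, data analysis.** The primary analysis is a ratio: "number of subjects with SVR-12; negative HCV RNA 12 weeks after completing Zepatier therapy) / (number of subjects treated with Zepatier post-heart transplantation". The denominator is everyone treated.
- **Section 10.4, Missing Data and Dropouts.** "For the primary end point, we will perform an analysis of completers only". The section adds "For patients lost to follow-up, we will use all the information available up to the time of loss to follow-up" and "We will also perform additional sensitivity analyses using imputation to assess the impact of missing data for the primary and secondary end points". It names no imputation method. On withdrawal it says: "Subjects who withdraw consent will no longer be followed in this protocol".
- **Section 10.5, Protocol Violations.** "Because all primary analyses will be intent-to-treat, it is essential that violations be kept to a minimum".

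Intention-to-treat also appears as the reason for continued follow-up in sections 8.3, 12.6 and 12.8. Section 12.6, for example, says: "Even if subjects are withdrawn from the study drug, outcome assessments will continue, allowing analysis by intent-to-treat".

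Section 10.3, where a governing rule would be expected, describes the population as recipients who develop de-novo HCV and gives no rule for a missing result. Section 9.1.1 defines SVR-12 by the HCV RNA result 12 weeks after the last dose and does not mention death or absent samples. For graft survival the plan does say how a death counts; section 9.2.2 reads: "with a graft failure defined as subject death, or re-transplantation within the first year post-transplantation". The primary end point has no equivalent statement.

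**The concern.** Read literally, the synopsis ratio keeps a treated subject with no SVR-12 result in the denominator and out of the numerator, so that subject counts as not cured. Section 10.4 as written takes the same subject out of both. These are different estimates of the primary result, and the plan does not choose between them.

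The undefined term adds a second ambiguity. If a completer is someone with an observed SVR-12, a subject who stops drug early but stays in follow-up is included. If a completer is someone who finished the course, that subject is excluded, although sections 12.6 and 12.8 keep such subjects under assessment for the sake of intention-to-treat.

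SVR-12 is the main efficacy output of a pilot that section 4.1 presents as the step before a funding application for a multi-center trial. Subjects lost from a completers-only rate need not resemble those who remain: section 12.10.1 lists death among the transplant risks, and subjects who withdraw consent are not followed. The trial is open-label with about 10 treated subjects, so the choice of denominator could be made with the results in view. A completers-only rate is 100% whenever no completer fails, however many treated subjects were lost before SVR-12.

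**Working it through.** **Inputs**

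- Treated subjects: 10 (section 3, Abstract). Replacement is described only for subjects who clear HCV without treatment (section 3; section 8.1.3.6), so the plan does not provide for replacing a treated subject who is lost.
- Number with no SVR-12 result, *m*, and number of observed virologic failures, *f*: assumptions, because the documents give no non-completion rate. I use *m* = 1 or 2 and *f* = 0 or 1.
- No planned figure can be reproduced. The 10 subjects come without a power, precision or dropout calculation.

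**Step 1. Compare the denominators**

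| Source | Denominator | Treated subject with no SVR-12 result |
|---|---|---|
| Synopsis | All treated | Stays in; not in the numerator |
| Section 10.4 | Completers (undefined) | Leaves the rate |
| Section 10.5 | Intent-to-treat (set undefined) | Not stated |

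The synopsis and section 10.5 can agree if intent-to-treat means all treated. Sections 10.4 and 10.5 can agree if a completer is a subject with an observed SVR-12 and intent-to-treat means regardless of adherence. In that second case the synopsis denominator still differs from section 10.4. No reading makes all three agree once a treated subject lacks a result, unless the section 10.4 analysis is not the primary one.

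**Step 2. Size of the difference**

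Completers (observed SVR-12) = (10 − *m* − *f*)/(10 − *m*). Synopsis ratio = (10 − *m* − *f*)/10. Best case, with all missing counted as cured = (10 − *f*)/10. Intervals are exact (Clopper-Pearson) 95%.

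| *m* | *f* | Completers only | Synopsis ratio | Best case | Gap, completers minus synopsis (points) |
|---|---|---|---|---|---|
| 1 | 0 | 9/9 = 100% (66.4–100) | 9/10 = 90% (55.5–99.7) | 100% | 10 |
| 2 | 0 | 8/8 = 100% (63.1–100) | 8/10 = 80% (44.4–97.5) | 100% | 20 |
| 1 | 1 | 8/9 = 88.9% (51.8–99.7) | 8/10 = 80% (44.4–97.5) | 90% | 8.9 |
| 2 | 1 | 7/8 = 87.5% (47.3–99.7) | 7/10 = 70% (34.8–93.3) | 90% | 17.5 |

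**Step 3. Effect of the undefined term alone**

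Suppose no result is missing, one subject stops drug early and has detectable HCV RNA at the SVR-12 sample, and the other nine are cured. If a completer is someone who finished the course, the rate is 9/9 = 100%. If a completer is someone with an observed SVR-12, it is 9/10 = 90%.

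**Step 4. How likely the difference is to appear**

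The chance that at least one of 10 has no SVR-12 result is 1 − (1 − *p*)^10, with *p* an assumed, independent per-subject probability.

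| Assumed *p* | Chance of at least one missing |
|---|---|
| 2% | 18% |
| 5% | 40% |
| 10% | 65% |
| 20% | 89% |

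**The case against.** The strongest reply is that only one sentence is out of line. The synopsis alone labels its formula the primary analysis, section 10.5 and the follow-up provisions point the same way, and section 10.4 is a missing-data section. It speaks of an analysis of completers, not the primary one, and then of further sensitivity analyses, so completers-only could itself be a sensitivity analysis. That reading is open and may be what was meant, but the text does not say so. The only analyses expressly labelled as sensitivity analyses are the imputation ones.

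Second, the damage may be nil. If every treated subject has an SVR-12 result and a completer is defined that way, the rates coincide. At assumed missing rates of 2% or 5%, no missing result is the likelier outcome (82% or 60%). This stands: the size is conditional. A subject who dies or is lost after the SVR-12 sample is not dropped, and a death before the first dose is outside both denominators.

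Third, section 10.2 promises CONSORT-style summaries, section 8.3 sets out retention measures and section 10.4 plans imputation. These make concealment harder and missing data fewer. They do not say which rate is primary or how SVR-12 is scored when absent, and section 10.2 does not expressly promise disposition after treatment starts.

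Finally, this is a single-arm pilot with no hypothesis test or success threshold. That limits the consequence to the reported rate and its interpretation, but that rate is the trial's principal efficacy result.

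**Conclusion.** The concern holds. The primary SVR-12 rate is not uniquely defined: section 10.4 conflicts with the synopsis denominator, and under one reading of completer with section 10.5 as well. With 10 treated and one or two missing results, following section 10.4 instead of the synopsis raises the reported rate by 8.9 to 20 points. Those counts are assumptions. With no missing result the gap is zero if a completer is a subject with an observed SVR-12, but it can still be 10 points if a completer is a subject who finished the course. No error rate is affected. The contradiction concerns the primary end point and can be removed at almost no cost, so it should be corrected before any SVR-12 results are analysed.

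**What to change.** State one primary analysis, identically, in the synopsis and sections 10.3 to 10.5:

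1. **Denominator:** every subject who took at least one dose of Zepatier, which makes the synopsis ratio explicit.
2. **Missing SVR-12:** death, withdrawal of consent or loss to follow-up without an SVR-12 result counts as non-response, with the reason listed for each subject beside the rate.
3. **Completer:** a subject with an observed SVR-12. Relabel the completers-only rate as a sensitivity analysis.
4. **Imputation:** replace the unnamed method with best-case and worst-case bounds, all missing counted as cured and all missing counted as failed.

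Two optional additions would help: an exact 95% confidence interval, and a rule that a later scheduled HCV RNA from the section 8.2.1 schedule, taken before any second-line treatment, may resolve a missing SVR-12.

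Making completers-only primary with a worst-case sensitivity analysis would also remove the contradiction. I prefer the synopsis ratio because it is the sponsor's own formula and keeps lost subjects in the rate.

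The cost is protocol and SAP wording, with no new data. The reported rate may be lower than under completers-only, and a death unrelated to HCV will count as non-response, which is why the reasons should be shown.

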7.1.4. Zepatier Initial Treatment Failures

Study subjects with treatment failure, defined as virologic breakthrough (when an undetectable viral load while on treatment becomes detectable) or virologic relapse (undetectable viral load after completion of treatment that during the 12-week post-treatment follow-up period becomes detectable) will be provided open-label Zepatier + Sofosbuvir (Sovaldi) 400 mg + Ribavirin (generic), renally dosed based on creatinine clearance per the manufacturer guidelines. Any subjects who experience treatment failure will repeat the original study lab visit and visit protocol once they begin their secondary treatment with Zepatier, sofosbuvir, and ribavirin, similar to

subjects initiating HCV treatment following heart transplantation. Prior to initiating treatment with this regimen, patients will have serum NS5A resistance (RAV) testing.

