8.3. Subject retention and drug adherence

We will enforce subject retention in several ways. We will record extensive contact information for each subject at their enrollment in the trial. This will include home, work, and cellular telephone numbers. The research staff will call before each study visit to remind the subject to attend. We will also obtain contact information of a family member or friend so that we can contact him/her if the subject does not answer his/her regular phone number.

An adequate record of receipt, distribution, and return of all study drugs must be kept. Subject adherence with the treatment and protocol includes willingness to comply with all aspects of the protocol, and to have blood collected for all safety evaluations.

The research staff and physician will explain the importance of adherence with the study protocol at each subject contact. If a subject fails to comply with a study visit, the staff will contact him or her by telephone. If this fails, the staff will send two certified express letters one week apart, to request follow-up.

We have considered how to minimize non-adherence with therapy. We will strongly emphasize the importance of complying with the study drug treatment. Nonetheless, we will perform pill counts at visits and record episodes when medication is withheld for any reason. If a subject has a serious adverse event (SAE) (whether related to study drugs or not), we will continue to follow-up with the subject for study assessments to assist with safety monitoring and to avoid the problems introduced by missing data. The inclusion of such follow-up data

will allow for analysis by intention-to-treat. If a study subject withdraws consent, he/she will no longer be followed.

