In order to preserve the integrity of the intention-to-treat analysis, even if the subject is withdrawn from the treatment portion of the protocol (either due to subject, physician, or investigator decision), it is imperative to continue with the scheduled follow-up assessments both for the safety of the subject and for completeness of data collection. This will be explained to potential subjects at the time of informed consent. The importance of adherence with study visits will be reinforced throughout the trial. If the treatment is permanently withdrawn, the subject will return to the center for safety assessment (history, physical examination, and clinical laboratories, if necessary).

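### Section 10.4 analyses SVR-12 in undefined completers only, against the intent-to-treat rule in 10.5 and the all-treated denominator in the synopsis; with 10 treated, each excluded non-responder adds about 10 points when nearly all the others respond

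*Combined protocol and SAP*

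**What the plan says.** The combined protocol and SAP describes the population for the primary endpoint in three places.

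- Section 10.4 (Missing Data and Dropouts): "For the primary end point, we will perform an analysis of completers only". It continues: "We will also perform additional sensitivity analyses using imputation to assess the impact of missing data for the primary and secondary end points". No imputation method is named, and no section defines a completer.
- Section 10.5 (Protocol Violations): "Because all primary analyses will be intent-to-treat, it is essential that violations be kept to a minimum".
- Synopsis, data analysis: the SVR rate is the number with negative HCV RNA 12 weeks after therapy, divided by the "number of subjects treated with Zepatier post-heart transplantation".

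Section 10.3 describes the primary analysis without giving a denominator. Other sections set up follow-up that serves an intention-to-treat analysis. Section 12.6 says "Even if subjects are withdrawn from the study drug, outcome assessments will continue, allowing analysis by intent-to-treat", and section 12.8 requires scheduled assessments to continue after treatment is withdrawn. The exception is withdrawal of consent. Section 8.3 says "If a study subject withdraws consent, he/she will no longer be followed".

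**The concern.** These statements give different denominators for one endpoint, and no text reconciles them. What 10.4 does to the estimate depends on what a completer is.

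- **Has the week-12 post-treatment RNA.** The setting of 10.4 (loss to follow-up, imputation) favours this reading. Treated subjects who die, are lost or withdraw consent then leave the denominator.
- **Finished the drug course.** This reading is less likely but not ruled out. Subjects stopped early would leave as well, although their visits continue and section 9.1.1 times SVR-12 from the last dose. A subject with on-treatment breakthrough, which section 7.1.4 counts as treatment failure and moves to second-line therapy, could also be dropped.

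On either reading, treated subjects leave the analysis for reasons that may be linked to a poor outcome. SVR-12 is the headline result of a pilot that section 4.1 presents as the step before a funding application for a multi-center randomized trial. With the rule left open, the denominator could be chosen after the results are known.

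**Working it through.** The plan has no figure to reproduce. It gives no target SVR rate, precision goal or dropout rate, and no derivation of the sample size. The check is therefore the arithmetic of changing the denominator.

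**Inputs**

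- Treated subjects: 10. The abstract (section 3) adds subjects until 10 have been treated. Section 8.1.3.6 replaces only those who clear HCV without treatment, and no rule replaces a treated subject who drops out.
- Endpoint: undetectable HCV RNA 12 weeks after the last dose (section 9.1.1).
- Expected rate, for context: 94-100% in earlier Zepatier trials (section 7.1).
- Excluded subjects without SVR-12, *k*: not given. Assumed to be 1, 2 or 3 of 10. Section 12.10.1 lists death and primary graft non-function among the transplant risks, so some loss is plausible, but it gives no usable rate.

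**Formulas**, with *s* subjects reaching SVR-12:

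- All treated: *s*/10
- Completers: *s*/(10 − *k*)
- Shift: *s*/(10 − *k*) − *s*/10
- Intervals: exact (Clopper-Pearson) 95%

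**Every completer responds**

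| *k* | All treated | Completers | Shift (points) |
|---|---|---|---|
| 1 | 9/10 = 90% (55.5-99.7) | 9/9 = 100% (66.4-100) | 10.0 |
| 2 | 8/10 = 80% (44.4-97.5) | 8/8 = 100% (63.1-100) | 20.0 |
| 3 | 7/10 = 70% (34.8-93.3) | 7/7 = 100% (59.0-100) | 30.0 |

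**One completer also fails**

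| *k* | All treated | Completers | Shift (points) |
|---|---|---|---|
| 1 | 8/10 = 80% (44.4-97.5) | 8/9 = 88.9% (51.8-99.7) | 8.9 |
| 2 | 7/10 = 70% (34.8-93.3) | 7/8 = 87.5% (47.3-99.7) | 17.5 |
| 3 | 6/10 = 60% (26.2-87.8) | 6/7 = 85.7% (42.1-99.6) | 25.7 |

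**At the expected rate.** If the completers' SVR rate is *p*, the all-treated rate is *p*(10 − *k*)/10 and the shift is *p* × *k*/10. For *p* from 0.94 to 1.00 this gives 9.4-10.0 points for *k* = 1, 18.8-20.0 for *k* = 2 and 28.2-30.0 for *k* = 3.

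**Where the shift is smaller.** For one exclusion the shift is *s*/9 − *s*/10 = *s*/90, which is 7.8 points at *s* = 7 and 5.6 at *s* = 5. If the one excluded subject did reach SVR-12 and all others respond, the comparison is 10/10 (69.2-100) with 9/9 (66.4-100). The estimate does not move and only precision is lost.

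**The case against.** The best defence is that 10.4 does not call the completers analysis primary. It promises an analysis of the primary endpoint in completers, within a section on missing data, and the word additional in the next sentence could mean that the completers analysis is itself one of the sensitivity analyses. Where the document does describe the primary analysis, in the synopsis and in 10.5, the population is all treated or intent-to-treat. Read literally, the synopsis formula already counts a treated subject without a week-12 RNA as a non-responder. That reading is possible, but 10.4 does not state it. The word only, the absence of any sensitivity label and the contrast with the imputation analyses all point to completers as the base case. An analyst following 10.4 as written would exclude treated subjects.

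Other points limit the weight of the concern.

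- The drug-completion reading is the weaker one. Section 7.1.4 classes breakthrough as treatment failure, and section 8.1.3.11 repeats the visits during second-line therapy. No text says such a subject would be left out.
- The 10-point figure needs nearly all other subjects to respond, and the exclusion counts are illustrations.
- The trial has no control, and the plan sets no success threshold for SVR, so no stated decision turns on the choice. The intervals overlap heavily.
- Section 10.2 promises CONSORT disposition summaries. With about 10 subjects, a reader could largely rebuild either rate, so a late choice would be hard to hide.

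These points lower the consequence. They do not settle which SVR rate is the primary result.

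**Conclusion.** The concern holds. Sections 10.4 and 10.5 and the synopsis cannot all govern the primary analysis, and the imputation analyses do not decide between them because they are only sensitivity analyses with no stated method. Followed as written, 10.4 removes treated subjects from the denominator and biases SVR-12 upward whenever those subjects did not reach it. The size is about 10 points per excluded non-responder at the SVR rates the protocol expects, and less if more completers fail.

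This rests on 10 treated subjects and on the excluded subjects being non-responders, and the documents do not say how many exclusions to expect. The trial remains interpretable, but its headline number is not uniquely defined. The text should be corrected before the analysis.

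**What to change.** Replace the completers sentence in 10.4, and match it in 10.3, with wording such as:

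> The denominator for the primary SVR-12 analysis is every subject given one or more doses of Zepatier, regardless of why treatment stopped. Each subject is scored on the HCV RNA taken 12 weeks after the final dose of the first-line course. A subject with no such result, or who started second-line treatment for virologic failure before it, is scored as a failure.

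Keep a completers analysis as a labelled sensitivity analysis and define completer. Replace the unspecified imputation with two bounds for the primary endpoint, one counting all missing results as failures and one counting them all as successes.

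This largely makes the synopsis formula explicit. It needs no new visits, samples or data. The reported SVR may be about 10 points lower for each treated subject without SVR-12. Counting missing as failure is conservative: one missing subject who was in fact cured would give 9/10 instead of 10/10, and the two bounds would show this.
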